In Part D, 8 subjects will be randomized in a 3:1 ratio to receive 5 consecutive daily doses of either 4 mg MRT5005 or placebo. Enrollment and treatment of subjects will not be staggered. Part D was added to the protocol (Version 5.0 dated 30 July 2020) to evaluate whether febrile reactions observed with higher doses (ranging from 8 mg to 24 mg) of MRT5005 are dose dependent or idiosyncratic.

Investigation of a daily dosing regimen in Part D is attractive given the estimated short half-life of CFTR mRNA (14 hours) and translated CFTR protein (29 hours). The anticipated safety of 4 mg administered daily for 5 days (20 mg total) can be predicted from the safety and tolerability of 20 mg administered as a single dose in Part A.

Enrollment and Treatment of Additional Groups

A SAD dose group may be repeated in a new group of subjects in Part A to further assess the safety of the dose level before escalating to the next higher dose level, or before allowing it to proceed from Part A (SAD) to Part B (MAD).

It is expected that no more than 1 additional group of 4 subjects will be enrolled into the study. Therefore, up to a maximum of 44 evaluable subjects may participate in the study.

Principal/Coordinating Investigators: [REDACTED]

Objectives:

Primary

- The primary objective of the study is to evaluate the safety and tolerability of single and multiple escalating doses of MRT5005 administered by nebulization to adult subjects with CF.

Secondary

- The secondary objective of the study is to evaluate the effect on percent predicted forced expiratory volume in 1 second (ppFEV₁) and other spirometry parameters after single and multiple escalating doses of MRT5005 administered by nebulization to adult subjects with CF.

Rationale:

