4.5.1. Reasons for Discontinuation and Individual Stopping Rules

Individual Subjects will be discontinued by the Investigator if they meet any of the stopping rules described below:

1. A significant febrile reaction defined as \geq Grade 2 fever (>39.0 °C) associated with systemic symptomatology (eg, body aches, malaise, nausea) within 24 hours following administration of IP.
2. An absolute decrease in predicted FEV1 of at least 25% compared to the baseline value (defined as the average of the Day -1 and Day 1 pre-dose values) during the 5-week treatment period in Part B or through Day 11 (1 week post-5th dose) in Part D that cannot be explained, in the opinion of the PI, by the underlying disease of CF and that is confirmed on 2 separate occasions at least 3 days apart
3. A suspected moderate to severe allergic/hypersensitivity reaction, including but not limited to anaphylaxis, generalized rash, edema or bronchospasm possibly related to drug treatment
4. Deterioration of liver function as explained below and in Section 8.1.4.1
 - a. Elevation of ALT or AST to >5 x ULN in a subject regardless of baseline value
 - b. Elevation of ALT or AST to >3 x ULN in a subject with a normal baseline or elevation of >3 x ULN from the subject's actual baseline if not normal, with the

appearance of fatigue, nausea, vomiting, right upper quadrant pain or tenderness, fever, rash, and/or eosinophilia (>5%).

c. Elevation of ALT or AST to >3x ULN in a subject with a normal baseline or elevation of >3x ULN from the subject's actual baseline if not normal, and total bilirubin >2x ULN or INR >1.5.

If any of the above criteria is met by a Part B or Part D subject who has not completed dosing with IP, treatment must be interrupted immediately and the Medical Monitor notified of this action.

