4.5.5. Part D Stopping Criterion

IP administration will be halted for all subjects in Part D if the following stopping criterion is met:

- a. Three subjects experience Grade 1 fevers (38.0 to 39.0 °C) associated with systemic symptomatology (eg, body aches, malaise, nausea) onset within 24 hours following administration of IP on ≥ 3 separate occasions.

To determine whether this dose group stopping rule has been met, the relevant data will be reviewed by the PSRC. The treatment assignment of one or more subjects may be unblinded at the request of the PSRC, as described in Section 3.4.1.2. Following this review, the PSRC will decide if the dose group and other ongoing higher dose groups will:

- Resume unchanged or
- Resume with modifications to the protocol or
- Be terminated.

The Sponsor is responsible for notifying the relevant regulatory authorities and the Investigator is responsible for promptly notifying the relevant IRB of the decision.

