5.1.1. Permitted Medications and Therapies

Subjects should remain on a stable medication regimen for CF from at least 28 days prior to the screening visit through the final study visit on Day 337 (± 3 days) in Part A, Day 365 (± 3 days) in Parts B, or Day 341 (± 3 days) in Part D of the study. These may include but are not limited to routine inhaled therapies directed at airway clearance and management of respiratory infections, such as bronchodilators, rhDNase (PULMOZYME), hypertonic saline, antibiotics, and steroids; and other routine CF-related therapies such as systemic antibiotics, pancreatic enzymes, multivitamins, and diabetes and liver medications. The timing of subject participation and routine treatment with cycled inhaled antibiotics will be left up to the discretion of the Investigator.

Hormone replacement therapies, thyroid hormone replacement therapy, and non-steroidal inflammatory drugs are also permitted.

Any other medications which are considered necessary for the subject's safety and well-being may be given at the discretion of the Investigator. For example, for subjects experiencing a pulmonary exacerbation, therapeutic interventions may include oral or intravenous administration of antibiotics, oral or parenteral nutritional support, frequent airway clearance techniques, augmented bronchodilator therapy, and corticosteroids.

Other specific medications permitted during the study are listed below:

- Hormonal contraceptives for females of childbearing potential administered according to the package insert (see Section 4.4.1).
- Lumacaftor/ivacaftor combination drug (ORKAMBI) or tezacaftor/ivacaftor combination drug (SYMDEKO). For Part D only: elexacaftor/tezacaftor/ivacaftor triple combination (TRIKAFTA). To be eligible, subjects must have been on stable treatment with these medications for at least 28 days prior to the screening visit and should remain on it for the duration of the study.

Subjects should remain on their routine CF therapies, which include but are not limited to airway clearance techniques.

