5.1.1.1. Modifications of Subject's Routine Pulmonary Medications and Therapies

If feasible for the subject, all spirometry testing should be performed “pre-bronchodilator” if the subject is receiving treatment with a short-acting beta-agonist or anticholinergic bronchodilator (eg, beta-agonist medication such as albuterol or anticholinergic agent such as ipratropium bromide). These medications should be withheld for at least 4 hours before spirometry testing (Section [7.5.2.12](#)).

On the days of IP dosing, the administration of IP should optimally occur within 2-3 hours after subjects have completed their routine pulmonary therapies (airway clearance and pulmonary medications) for the day. For subjects whose routine airway clearance therapies do not include an inhaled short-acting beta-agonist (or it is not given within the 2 to 3 hour window prior to IP administration), albuterol (2 to 4 puffs) will be administered via metered-dose inhaler approximately 20 minutes before nebulization with IP to minimize any bronchoconstrictive effects. Note that administration of short-acting beta-agonist via nebulization is also permitted at the discretion of the Investigator.

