5.1.2. Prohibited Medications

Specific medications not permitted during the study are listed below:

- Ivacaftor monotherapy (KALYDECO)
- Parts A and B only: Triple-combination therapy (TRIKAFTA)

Starting on or switching to TRIKAFTA is acceptable during the follow-up period; however, subjects should not start/switch until at least 2 months after their last dose of study drug so as not to confound the interpretation of the primary and secondary endpoints.

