Treatment-emergent febrile reactions and hypersensitivity reactions will be presented as a count of febrile reactions, febrile reactions by severity, hypersensitivity reactions, and hypersensitivity reactions by severity. Additionally, the table will reflect the count and percentage of subjects experiencing the following: any febrile reaction, any febrile reaction by severity, any hypersensitivity reaction, and any hypersensitivity reaction by severity. The summary will be for all subjects in the safety analysis set by dose group for each study part. In addition, the summary of treatment-emergent febrile reactions and hypersensitivity reactions will be presented for all subjects in the safety analysis set for the study overall by pooled treatment group. Febrile reactions will be identified based on a preferred term of body temperature increased or preferred term of pyrexia within the 24 hours after completion of

nebulization on any dosing day with at least one other systemic symptom reported as a preferred term of headache, arthralgia, myalgia, fatigue, chills, nausea, or vomiting within the 24 hours after completion of nebulization on any dosing day. Severity grade for febrile reactions will be based on the maximum severity of the preferred terms comprising the febrile reaction. Hypersensitivity reactions will be identified based on a preferred term of hypersensitivity within the 24 hours after completion of nebulization on any dosing day.

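### Antipyretics are unrestricted on dosing days and not linked to the febrile-reaction counts, so the fever stopping rules and Tables 14.3.2.4 and 14.3.2.5 can understate the reaction Part D was added to study

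*Protocol*

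**What the plan says.** **Medication.** Protocol 5.1.1: "Hormone replacement therapies, thyroid hormone replacement therapy, and non-steroidal inflammatory drugs are also permitted". I read the printed drug class as NSAIDs. No dose, timing or dosing-day condition follows. The same section adds "Any other medications which are considered necessary for the subject's safety and well-being may be given at the discretion of the Investigator". Section 5.1.2 opens "Specific medications not permitted during the study are listed below" and names only CFTR modulators. For bronchodilators, by contrast, 5.1.1.1 does give a timing rule: "These medications should be withheld for at least 4 hours before spirometry testing".

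**Stopping rules.** Section 4.5.1 (rule 1) acts on fever above 39.0 °C "associated with systemic symptomatology (eg, body aches, malaise, nausea) within 24 hours following administration of IP". Section 4.5.4(a) needs two such subjects in a dose group. Section 4.5.5 needs three Part D subjects with fever of 38.0 to 39.0 °C plus symptoms, "onset within 24 hours following administration of IP", on at least three separate occasions.

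**Analysis.** SAP 9.4: "Febrile reactions will be identified based on a preferred term of body temperature increased or preferred term of pyrexia", together with at least one listed systemic symptom, within 24 hours after nebulization. Table 14.3.2.4 gives the counts by dose group within each study part, and Table 14.3.2.5 gives them for pooled MRT5005 and pooled placebo.

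**Purpose.** The Synopsis says Part D was added "to evaluate whether febrile reactions observed with higher doses (ranging from 8 mg to 24 mg) of MRT5005 are dose dependent or idiosyncratic".

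**The concern.** Recorded fever is a necessary element of each of the three stopping rules and of the SAP definition. It is not sufficient, since systemic symptoms are also required. A subject who takes an antipyretic before dosing, or at the first chill, may have chills, myalgia or nausea but no qualifying temperature and no fever term. That subject counts toward none of the rules and appears in neither febrile-reaction table.

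No planned display connects antipyretic use to a dosing day or to a febrile reaction. SAP 9.6.3.4 tabulates medication by ATC class and drug name. Listing 16.2.14.1 shows dates and study days but no clock time. A low febrile count at 4 mg could then reflect the lower dose, antipyretic use, or both, and the planned tables would not tell them apart. With six active subjects in Part D (SAP 2.5), a few missed reactions would change the picture.

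**Working it through.** The documents give no operating characteristics for the fever rules, so there is no plan figure to reproduce.

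**Counts.** Protocol 2.2.3 reports febrile reactions in 1 + 1 + 1 + 3 + 1 = 7 subjects. Six of these were in Part A, where 4 groups × 3 = 12 subjects were active, so 6/12 = 50%. Part D has 8 × 3/4 = 6 active subjects.

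**Illustration 1: cover after a first fever (rule 4.5.5).** Assumptions:
- the rule means three subjects, each with at least 3 fever days out of 5;
- doses are independent;
- only the 6 active subjects can be febrile;
- the per-dose chance of a qualifying fever is p until the first fever and p2 afterwards, in every subject.

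Per subject: s = Σ(k = 1 to 3) (1−p)^(k−1) · p · P[Bin(5−k, p2) ≥ 2]. Trigger: P[Bin(6, s) ≥ 3].

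- p = 0.5, p2 = 0.5: s = 0.5×0.6875 + 0.25×0.5 + 0.125×0.25 = 0.500; trigger 0.656.
- p = 0.5, p2 = 0.25: s = 0.5×0.2617 + 0.25×0.1562 + 0.125×0.0625 = 0.178; trigger 0.07.

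| p | No cover | Later fevers halved | Later fevers quartered |
|---|---|---|---|
| 0.3 | 0.059 | 0.002 | <0.001 |
| 0.5 | 0.656 | 0.07 | 0.0025 |
| 0.7 | 0.992 | 0.399 | 0.026 |

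The chance that a subject has any fever is 1 − (1−p)^5, for example 0.97 at p = 0.5. It does not involve p2, so this model leaves the count of subjects with any febrile reaction unchanged.

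**Illustration 2: use that hides a reaction altogether.** Let p now be the chance that an active subject has a true febrile reaction, and m the share of reactions never recorded as fever. The counted rate is q = p(1−m), and the chance of no counted reaction among 6 is (1−q)^6.

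- p = 0.33: (0.67)^6 = 0.09 at m = 0; (0.835)^6 = 0.34 at m = 50%.
- p = 0.50: (0.50)^6 = 0.02 at m = 0; (0.75)^6 = 0.18 at m = 50%.

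All values of p, p2 and m are assumptions. The documents report no antipyretic use.

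**The case against.** The strongest reply is that the signal remains visible elsewhere and that the medication data already exist. Much of this stands.

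- SAP 9.4 lists all adverse events during nebulization or within 24 hours after it, with or without fever. CRP is plotted by subject, and Part D inflammatory markers are measured (Protocol Table 8). Protocol 3.2.3 lets the PSRC and Sponsor stop Part D for poor tolerability without any temperature trigger. A reader might infer that the reaction would be hidden altogether; the documents do not support that.
- Listing 16.2.14.1 also shows study day, indication and a *Taken for AE?* column, and Table 8 collects medication before and 2 hours after each Part D dose. Linkage by day is therefore possible. It is simply not planned, and same-day preventive use cannot be ordered against a fever.
- A reader might infer that the Body Temperature Recording Log has no place for antipyretics. Neither the log nor the CRF is in the documents, so this cannot be said.
- A reader might infer that the later groups are biased toward fewer fevers because fever was by then expected. The documents give no usage data, and home thermometers (Protocol 7.2.2, 7.3.2 and 12) push ascertainment upward in those groups.
- SAP 9.4 sets no temperature cut-off, so staying below 38.0 °C does not by itself remove a subject from the tables. What matters there is whether a fever term is reported.
- Section 4.5.5 can also be read as three occasions in total. Under that reading, cover after a first fever leaves Illustration 1 unchanged. At p = 0.33 the uncovered trigger is only about 0.1 in any case.
- Section 5.1.1 does not contradict the stopping rules: one permits a drug and the others define triggers.

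What survives is that neither the rules nor the febrile-reaction tables take account of antipyretic use.

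**Conclusion.** The point holds as a limited gap in ascertainment and analysis, and it is worth correcting. Unrestricted antipyretic use can lower the febrile counts that carry the dose-dependent versus idiosyncratic question, and no planned display would show it. The effect on the repeat-based Part D rule could be large: 0.66 to 0.07 at a per-dose rate of 0.5, and 0.06 to 0.002 at 0.3. Those figures rest on universal cover after a first fever, a halving of later fevers, independent doses and one reading of 4.5.5. They do not bear on the number of subjects with any febrile reaction. That number falls only if a subject's reactions go unrecorded altogether, as in Illustration 2. The actual size is unknown because antipyretic use is unknown.

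**What to change.** In Tables 14.3.2.4 and 14.3.2.5, link the medication CRF (dates, indication, *Taken for AE?*) to dosing days and add:

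1. subjects, and dosing days, with NSAID, other antipyretic or systemic steroid use on the dosing day or the day after;
2. as a sensitivity count, subjects with a febrile reaction, or with a listed systemic symptom within 24 hours plus antipyretic use, whether or not fever was recorded.

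For any dosing still to come, record the clock time of and reason for antipyretic use on dosing days. State an attribution rule for Part D, where daily dosing makes the windows overlap; for example, assign use to the most recent dose.

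Whether antipyretics are allowed around dosing, and how a covered day counts toward 4.5.1, 4.5.4 and 4.5.5, is for the sponsor and the PSRC to state. No clinical rule is proposed here.

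Cost: a little programming and a small recording burden. Groups already dosed will have day-level precision only.

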5.1.1.1. Modifications of Subject's Routine Pulmonary Medications and Therapies

If feasible for the subject, all spirometry testing should be performed “pre-bronchodilator” if the subject is receiving treatment with a short-acting beta-agonist or anticholinergic bronchodilator (eg, beta-agonist medication such as albuterol or anticholinergic agent such as ipratropium bromide). These medications should be withheld for at least 4 hours before spirometry testing (Section [7.5.2.12](#)).

On the days of IP dosing, the administration of IP should optimally occur within 2-3 hours after subjects have completed their routine pulmonary therapies (airway clearance and pulmonary medications) for the day. For subjects whose routine airway clearance therapies do not include an inhaled short-acting beta-agonist (or it is not given within the 2 to 3 hour window prior to IP administration), albuterol (2 to 4 puffs) will be administered via metered-dose inhaler approximately 20 minutes before nebulization with IP to minimize any bronchoconstrictive effects. Note that administration of short-acting beta-agonist via nebulization is also permitted at the discretion of the Investigator.

5.1.2. Prohibited Medications

Specific medications not permitted during the study are listed below:

- Ivacaftor monotherapy (KALYDECO)
- Parts A and B only: Triple-combination therapy (TRIKAFTA)

Starting on or switching to TRIKAFTA is acceptable during the follow-up period; however, subjects should not start/switch until at least 2 months after their last dose of study drug so as not to confound the interpretation of the primary and secondary endpoints.

5.2. Concomitant Surgical Procedures

Surgical procedures (eg, ventral hernia repair, tooth extraction, sinus surgery) that occur from the date of informed consent signing through the final study visit must be recorded on the Concomitant Surgical Procedure CRF page. The date(s) of the procedure and the indication for the procedure will be documented. The indication must have a corresponding entry on the Medical History page (for pre-existing conditions) or Adverse Event page (for new or worsened pre-existing conditions), unless the surgical procedure was prophylactic in nature (eg, PICC line placement for CF cleanout).

For any unplanned hospitalization or prolongation of hospitalization, the procedures for safety reporting should be followed (see Section [8](#)).

6. INVESTIGATIONAL PRODUCT

See the Pharmacy Manual for detailed instructions on the preparation of the IP.

Information on the preparation of study product is provided in Section 6.2.2. Labeling and packaging descriptions are provided in Section 6.3.1, and storage conditions are described in Section 6.3.2.

6.1. Identity of Investigational Product

6.1.1. MRT5005

MRT5005 is a lipid nanoparticle suspension consisting of [REDACTED] mRNA ([REDACTED] mRNA), the active drug substance, formulated with the [REDACTED] lipids, [REDACTED]. MRT5005 is dosed based on its content of [REDACTED] mRNA.

MRT5005 will be supplied as a sterile suspension in single-use vials. Each vial contains approximately 3.2 mL of MRT5005 at a concentration of 0.6 mg/mL of [REDACTED] mRNA. An InnoSpire Go nebulizer will be used to administer MRT5005 to the lungs by nebulization. MRT5005 is dosed based on its content of [REDACTED] mRNA.

Refer to the MRT5005 Investigator's Brochure for further information about the drug product.

6.1.2. Placebo Comparator

Sterile normal saline solution (Sodium Chloride Inhalation Solution, USP 0.9%) will be used as the placebo comparator.

6.1.3. Blinding the Treatment Assignment

This study will be conducted as a randomized, double-blinded, placebo-controlled trial. The blinding of the study will be maintained as described below.

The Investigators and all study staff involved in the evaluation of subject eligibility, administration of IP, and assessment of study outcomes will be blinded to treatment assignment (MRT5005 vs. placebo within each dose group). All subjects and their families, as well as Sponsor personnel in direct contact with the study center, will also be blinded. The blinded Investigator and study staff must not be allowed to know the IP assigned to any study subject and must not be allowed to see the randomization code; IP, its containers or its preparation; or treatment records until planned interim analyses are completed, as specified in Section 6.2.3. In addition, study staff who will be administering IP (and monitoring the subject for any signs or symptoms of respiratory distress) will be instructed not to open the nontransparent medication cup of the InnoSpire Go to visualize the study drug as MRT5005 will appear different than the normal saline placebo (see below). As such, all relevant individuals will be blinded to treatment assignment, thus maintaining the double-blinded conduct of the study.

As the MRT5005 suspension and normal saline placebo will appear different (normal saline will also be supplied in its commercial presentation and stored at a different temperature), designated unblinded members of the study staff and/or pharmacy will be responsible for preparing and dispensing IP into the nebulizers. The unblinded members of the study staff and/or pharmacy will also be responsible for randomizing subjects once their eligibility has been confirmed. The unblinded members of the study staff and pharmacy will be fully trained in their study-related responsibilities. They will not participate in any other part of the study and will maintain the subject treatment assignments in strict confidence. Their roles will be documented on the study center's delegation of authority log.

Sponsor designated unblinded monitors will be permitted access to monitor the IP preparation, dispensing, and accountability records as well as randomization codes during the study.

Circumstances in which treatment assignments may be broken are presented in Section [6.2.3](#).

